**8. Study Methods**

- **Population of study:** (Please provide all details regarding participants including gender, age range and disease conditions. Also indicate if this protocol involves children, prisoners, pregnant women or cognitively impaired or mentally disabled subjects)

Two groups with confirmed laboratory and ultrasonography diagnosis of PCOS , First group will include 30 eyes of 30 females in childbearing period (18-40 years old) scheduled for treatment for non- fertility indications with oral contraceptive pills (as a first line of treatment), and the second group will include 30 eyes of 30 females in childbearing period (18-40 years old) scheduled for treatment with Clomiphene citrate (as a first line of treatment), for fertility indications.

- **Study location:** (Please provide where the study will be conducted and from where study participants will be recruited)

Patients will be recruited from gynecology and dermatology Kasr Al-Ainy clinics and will undergo their ophthalmic examination and investigations at the department of ophthalmology, Kasr Al-Ainy school of medicine.

- **Inclusion criteria:**

1. Females at child bearing period (18-40 years old).
2. Patients recently diagnosed with polycystic ovarian syndrome.

- **Exclusion criteria:**

1. Patients who were diagnosed with Dry eye disease.
2. Patients who were treated with hormonal replacement therapy, Metformin, Aromatase inhibitors, clomiphene citrate or androgen antagonists.
3. Patients who underwent ocular surgeries.
4. Patients with history of diabetes mellitus or hypertension.

- **Methodology in details:**

Two groups with confirmed laboratory and ultrasonography diagnosis of PCOS, First group will include 30 eyes of 30 females in childbearing period (18-40 years old) scheduled for treatment for non- fertility indications with Estradiol valerate / Norgestre tablets for six months, The second group will include 30 eyes of 30 females in childbearing period (18-40 years old) scheduled for treatment with Clomiphene citrate for fertility indications for 6 months.

- Follicle stimulating hormone (FSH), luteinizing hormone (LH) , androgen, estrogen, progesterone , fasting insulin and neutrophil to lymphocyte ratio (NLR) will be obtained.
- The two groups will undergo complete ophthalmic examination including :

\*Full history.

\*Standard Patient Evaluation of Eye Dryness Questionnaire (SPEED) in order to quickly track the progression of dry eye symptoms over time.

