\*Manifest refraction.

\* Corrected distance visual acuity.

\* Anterior segment examination using slit lamp, Schirmer's test and tear film breakup time test.

\* Fundus examination.

\* Measuring central corneal thickness (CCT) using Corneal pachymetry.

•Beside Schirmer's test, tear film breakup time test and fluorescein break-up patterns, Dry eye assessment will be performed using Dry Eye Diagnostic System device (D130, Medi-Works Precision Instruments; Shanghai, China). Device to have a Dry eye diagnosis brings out an automatic result of non-invasive break up test (NIBUT) and tear meniscus height after taking one video. It is a fully automatic analysis system to provide efficient quantified evaluation for the overall stability of the tear film. Also it uses identification system that depicts the tear meniscus area and measures the tear height automatically.

The device also automatically analyses the meibomian glands, lipid layer thickness, and eyelid margin. The built-in infrared lighting system helps to obtain the enormous image scope of the meibomian glands. Finally the device identifies and calculates percentages of

conjunctival congestion and ciliary congestion, Thus evaluating the severity of eye congestion. If the degree of severity of eye congestion is more than two, it is abnormal.  
\*Examination and laboratory tests will be done before, 3 months after starting treatment and after finishing the treatment course.

- **Intervention:**

☒ Diagnostic intervention (please describe):

Imaging ocular surface using dry eye diagnostic system.

☐ Therapeutic intervention (please describe):

☐ No intervention

- **Does the research involve?**

☒ Human participants

☐ Biological samples/Tissues

☐ Identifiable private data/Information

- **Type of consent of study participants:**

☒ Written consent

[figure not shown]
☐ Oral consent

☐ No consent needed (Please justify)

- **Potential risks:**

(Please mention all risks involved even mild ones as pain, discomfort, chance of infection or psychological effects)

1- No possible risks

- **Confidentiality of data:** (Please explain how privacy and confidentiality of data and records will be maintained)
- Names and private data of patients will not be published, only the results of the study will be analyzed and published.

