### 9- Study outcomes:

- **Primary outcomes** (Most important measurable outcomes)
  - 1- Measuring changes in meibomian glands function, break up time, tear meniscus height, and lipid layer thickness in polycystic ovarian syndrome and with different drugs used in managing it.
- **Secondary outcome parameters** (other outcomes to be assessed)
  - 1- Measuring eye lid margin, conjunctival hyperemia, and ocular surface staining in polycystic ovarian syndrome and with different drugs used in managing it.
  - 2- Measuring the central corneal thickness (CCT) changes in polycystic ovarian syndrome and with different drugs used in managing it.

**10- Sample size** (number of study subjects included and justification including the clinical and statistical assumptions supporting sample size calculation)

$$\left( \frac{Z_{a/2} + Z_B}{P_1 - P_2} \right)^2 (p_1 q_1 + p_2 q_2)$$

(Takazawa & Morita, 2020)

n = sample size

Z a/2 (The critical value that divides the central 95% of the Z distribution)

ZB (The critical value that divides the central 20% of the Z distribution)

p1 = prevalence in case group

p2 = prevalence in control group.

q = 1-p

Epi Info STATCALC was used to calculate the sample size by considering the following assumptions:- 95% two-sided confidence level, with a power of 80%. &  $\alpha$  error of 10% . The final maximum sample size taken from the Epi- Info output was 26. Thus, the sample size was increased to 30 subjects with total 30 eyes in each group to assume any drop out cases during follow up.

[figure not shown]
**11- Statistical analysis** (Please describe your data analysis plan)

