Data management and analysis will performed using Statistical Package for Social Sciences (SPSS). Median and range for non-parametric measures and ordinal (scores) data. Numerical data will be presented as means  $\pm$  standard deviations (SD). Categorical data will be presented as number and percentages %. Pairwise comparisons between the two groups for normally distributed variables will be done using the Student's t-test; the Mann-Whitney test, a nonparametric test equivalent to the t-test, will be used in non-normally distributed variables. The Repeated measures ANOVA test will be used to compare the effect change within and between the study groups at different visits. The chi-square test or the Fisher's exact test will be used to compare between the groups with respect to categorical data. All p-values will be two-sided. P-values  $< 0.05$  will be considered significant

**12- Source of funding:** (Please include source of funding even if self funding)

- Faculty of Medicine, Cairo University ☐
  - Other sources: ☐
- Please specify: Self-funding

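### Section 11 plans repeated measures ANOVA without naming the term that compares the drugs or a rule for missed visits; a mixed model with a named month-6 group-by-visit contrast would settle both.

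*Combined protocol and SAP*

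**What the plan says.** - **Test over visits.** Section 11 gives one method: "The Repeated measures ANOVA test will be used to compare the effect change within and between the study groups at different visits". It does not name group, visit or group-by-visit as the result to report. It also does not say whether the pre-treatment visit is a repeated level or a covariate.
- **Visits.** Section 8 sets three: "Examination and laboratory tests will be done before, 3 months after starting treatment and after finishing the treatment course". The course lasts six months ("scheduled for treatment with Clomiphene citrate for fertility indications for 6 months"), so the last visit falls at about month 6.
- **Primary outcome.** Section 9 begins "Measuring changes in meibomian glands function, break up time, tear meniscus height, and lipid layer thickness in polycystic ovarian syndrome" and goes on to the different drugs. It gives no primary timepoint or contrast.
- **Two-group tests.** Section 11 adds: "Pairwise comparisons between the two groups for normally distributed variables will be done using the Student's t-test", with Mann-Whitney for non-normal variables. It does not say whether these tests apply to a visit or to a change from baseline.
- **Distribution.** Section 11 expects data that are not normal ("Median and range for non-parametric measures and ordinal (scores) data") but names no method for such data over repeated visits.
- **Drop-out.** Section 10 calculates 26 per group, and "the sample size was increased to 30 subjects with total 30 eyes in each group" to allow for drop-out. There is no missing-data rule and no analysis set. SPSS is the stated software; the procedure is not named.

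**The concern.** The primary question is whether ocular surface measures change differently under the two treatments. A two-group repeated measures ANOVA gives two tests that involve group, and they answer different questions. The main effect compares group means averaged over all visits, including the one before any drug was taken. The group-by-visit term compares the change. The plan leaves the choice open.

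The choice matters more than usual here because the groups are not randomised. They are defined by indication (non-fertility or fertility), so a difference before treatment is plausible. It would pass straight into the main effect, where it could imitate, hide or reverse a drug effect.

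The second issue is missed visits. Classical repeated measures ANOVA, the usual SPSS GLM form, uses only women with every visit. The plan expects losses but does not say what happens to the data already collected from those women.

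**Working it through.** **Inputs from the documents:** three visits, one of them pre-treatment (Section 8); 26 per group raised to 30 (Section 10); two-sided tests at 0.05 (Section 11).

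**Assumptions, because the documents give no effect size, SD or correlation:** SD 1 at each visit; equal correlation r between visits, from 0.3 to 0.8; a drug difference of 0.75 SD, chosen near the 0.72 SD detectable with 30 per group at 80% power: (1.960 + 0.842) × √(2/30) = 0.72.

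**1. The plan's own figure.** The 26 can be neither confirmed nor refuted, because the two prevalences in the formula are not given. The step to 30 is coherent: 4/30 = 13.3%, and 26/(1 − 0.133) = 30.

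**2. What the main effect targets.**
- Constant effect d at both follow-ups: (0 + d + d)/3 = 2d/3. For d = 0.75 this is 0.50 SD.
- Effect building linearly (0.375, then 0.75): (0 + 0.375 + 0.75)/3 = 0.375 SD, half the final effect.

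**3. Power at 30 per group, 0.75 SD at both follow-ups.**
- Main effect: the three-visit mean has SD √((1 + 2r)/3); normal approximation.
- Group-by-visit: noncentral F with 2 and 2(2n − 2) = 116 df and λ = (n/2) × Σ(dⱼ − mean d)²/(1 − r). The deviations are −0.50, 0.25, 0.25, so the sum of squares is 0.375. At r = 0.5, λ = 15 × 0.375/0.5 = 11.25.

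| r | Main effect | Group-by-visit |
|---|---|---|
| 0.3 | 75.5% | 70.8% |
| 0.5 | 66.0% | 85.1% |
| 0.7 | 58.1% | 97.6% |
| 0.8 | 54.8% | 99.8% |

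The change term is the stronger one except at r = 0.3.

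**4. Baseline gap with no drug effect.** With a 0.5 SD gap present at all three visits and 30 per group, 4,000 simulated trials per setting gave:
- main effect significant in 65% (r = 0.5) and 57% (r = 0.7);
- group-by-visit significant in about 5% at both correlations, which is the nominal level.

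**5. Missed visits under complete-case analysis.**
- If 4 of 30 per group leave after month 3, then 8 women × 2 visits = 16 collected records go unused.
- Going from 30 to 26 complete women per group at r = 0.5 gives λ = 13 × 0.375/0.5 = 9.75. Group-by-visit power falls from 85.1% to 79.2%.
- If women instead miss each post-treatment visit independently with probability 13.3%, then 30 × 0.867² ≈ 23 per group are complete, fewer than the 26 calculated. At 5% and 20% the figures are about 27 and 19.

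**The case against.** The strongest reply is that the plan never says groups will be compared on an average over visits. Its sentence speaks of the change, between groups, at different visits, which reads at least as naturally as group-by-visit. On that reading nothing is diluted and an unchanging baseline gap cancels.

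A reader might go further and infer that repeated measures ANOVA itself costs power here. The documents do not support that. With an assumed 0.79 SD at both follow-ups and 26 per group, group-by-visit power is 84%, 91% and 97% at r = 0.5, 0.6 and 0.7. A simple comparison of change scores gives about 80%, 88% and 95%. At r = 0.3 even the main effect (72%) beats the change score (66%).

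A reader might also infer that the plan has chosen to drop women with missed visits. It has not: deletion belongs to the usual GLM routine, and SPSS also fits mixed models. The 16 records are the figure for the case in which all eight women leave after month 3. Moreover, 26 complete women per group is the number Section 10 calculated, so the fall from 85% to 79% is modest and partly unavoidable.

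All of this stands, and it limits the point to what is left unspecified. It does not close the gap. The text permits either ANOVA term, and under a baseline gap the two can lead to opposite conclusions. The planned t-tests do not settle the matter, because the plan does not say what they are applied to. Silence on missed visits leaves the default of whichever procedure is used.

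**Conclusion.** The point holds as a gap in specification with a cheap and better alternative; it is not a demonstrated loss of power. Three things are missing: the ANOVA term that answers the between-drug question, the handling of missed visits, and a repeated-visit method for ordinal or non-normal outcomes.

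The larger risk is reporting the main effect in non-randomised groups, where a pre-treatment difference alone can produce a significant result. The complete-case loss is smaller. The two-thirds dilution follows from the visit schedule when the effect is constant at both follow-ups. The power and false-positive figures depend on the assumed effects, gap and correlations, and on equal correlation between visits. The loss of records further depends on the classical procedure being the one used.

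**What to change.** In Section 11, replace repeated measures ANOVA with a linear mixed model (SPSS MIXED) on all observed visits, with group, visit and group-by-visit as fixed effects and a covariance structure stated in advance. Name the end-of-treatment (month-6) group-by-visit contrast, which is the difference between groups in change from the pre-treatment visit, as the between-drug result. Report it with its 95% CI, and state that the group main effect is not that result. For ordinal or clearly skewed outcomes, name a matching repeated-measures method for the same contrast, such as GEE or a bootstrap CI.

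The cost is a few sentences, a different SPSS menu and slightly more analysis work, with no new data. Two limits should be stated. The model keeps the earlier visits of women who leave but cannot recover their missing month-6 values, and it assumes that missingness depends on observed data. It also does not remove confounding by indication.

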**13- Time plan:**

[figure not shown]
- When to start? Immediately after acceptance.
- When expected to finish? After 18 months
- When to publish? After 18 months

